	11.1 Sponsor approval	
	11.2 Confirmation of Capacity and Capability	
	11.3 Investigators' responsibilities	
	11.4 Monitoring by sponsor	
	11.5 Indemnity	
12.	Data protection and participant confidentiality	30
	12.1 Data protection	30
	12.2 Data handling, storage and sharing	30
13.		
14.	References	
15.	Amendments to protocol	33

Glossary / abbreviations

AE Adverse event - any undesirable event in a subject receiving treatment according to

the protocol, including occurrences which are not necessarily caused by or related to

administration of the research procedures.

AMIC Autologous matrix-induced chondrogenesis

AR Adverse reaction – any undesirable experience that has happened a subject while

taking a drug that is suspected to be caused by the drug or drugs

BTC Bristol Trials Centre Cl Chief Investigator

CONSORT Consolidated Standards of Reporting Trials

CRF Case report form

CTEU Clinical Trials and Evaluation Unit
DMSC Data Monitoring and Steering Committee

GCP Good Clinical Practice
GP General Practice

HES Hospital Episode Statistics
HRA Health Research Authority
HRQoL Health Related Quality of Life
HTA Health Technology Assessment

IKDC International Knee Documentation Committee

ITT Intention-to-treat

KOOS Knee injury and Osteoarthritis Outcome Score

LPLV Last patient last visit

MCID Minimal clinically important difference

MHRA Medicines and healthcare products regulatory agency

MRC Medical Research Council
MRI Magnetic Resonance Imagining

NHS National Health Service

NICE National Institute for Health and Care Excellence

NIHR National Institute for Health Research

PEP-R Patient Experience Partnership in Research

PIL Patient information leaflet
PI Principal Investigator

PSS Personal social services perspective

RCT Randomised controlled trial REC Research ethics committee

SAE Serious adverse event - events which result in death, are life threatening, require

hospitalisation or prolongation of hospitalisation, result in persistent or significant

disability or incapacity.

SAR Serious adverse reaction SD Standard deviation

SOP Standard operating procedure SSA Site Specific Assessment

SSAR Suspected serious adverse reaction

SUSAR Suspected unexpected serious adverse reaction - an untoward medical occurrence

suspected to be related to a medicinal product that is not consistent with the applicable

product information and is serious.

TMF Trial Master File
TMG Trial management group
TSC Trial steering committee

UKCRC The UK Clinical Research Collaboration
WPAI Work Productivity and Activity Impairment

QALYs Quality adjusted life years

1. Trial summary

Knee injuries are common and can lead to pain and disability. Injuries to the smooth cartilage that lines the ends of the bone in joints can cause ongoing problems as the cartilage does not have a blood supply and rarely heals once injured. 10,000 people a year in the UK have a severe articular cartilage injury that warrants surgical treatment. There are two main ways in which these injuries can be treated surgically, the first is to try to address the symptoms without trying to restore the cartilage; such as cleaning (debriding) the area or replacing the damaged area with an implant. The other way is to try to repair or restore the cartilage in the damaged area. Cartilage does not grow back on its own, so an operation known as "microfracture" can be performed to encourage the cartilage to grow. A surgical tool is used to make perforations in the bone in the damaged area which allows blood and bone marrow to seep out of the holes, encouraging healing. A "scaffold", which is usually made of the same material that makes up most of the cartilage (collagen), can be added, termed Autologous Matrix-Induced Chondrogenesis (AMIC). The scaffold is secured in place and acts as a template for new cartilage to form on. It is not clear if using a scaffold improves the outcome for patients. Using scaffold makes the operation more complex (approximately 20 minutes longer) and the cost of the scaffold is approximately £900, so it is important to establish if adding a scaffold results in a better outcome for patients and is cost-effective for the NHS.

The study will find out whether adding the scaffold is worthwhile or not for patients with knee articular cartilage injuries. Over 2 years we will aim to recruit 176 patients, who will be randomised into two equal sized groups from at least 16 hospitals. One group of patients will have microfracture alone and the other will have microfracture plus scaffold (AMIC). Everything else will be the same for all patients. Both groups will be followed for 2 years by clinical review. We will collect information about quality of life, symptoms and pain in the knee, complications of surgery, need for further surgery and costs to the NHS and patients.

2. Background

Up to 10,000 symptomatic articular cartilage injuries occur each year, mostly in patients under 35 years of age. There are two main treatment modalities, the first aims to restore cartilage with microfracture, with or without scaffold insertion, or cellular methods and the second aims to improve symptoms without restoring cartilage. For young patients, restoring cartilage is felt to be more appropriate. Microfracture involves penetrating the subchondral bone in the area of injury to release fibrin and stem cells, which leads to the development of some parts of normal cartilage, but not all. It has been suggested that results may be better if a scaffold is used to help the repair (AMIC). Scaffolds are safe to use but there is no definitive evidence that it improves results, as summarised in this most recent review.(1)

3. Rationale

Articular (hyaline) cartilage is a very specialised structure which allows low friction movement with very low wear rates.(2, 3) Injuries to the articular cartilage in the knee are common, particularly in patients under 35 years of age. The National Institute for Health and Care Excellence (NICE) estimates that around 10,000 patients per year in the UK suffer from cartilage damage warranting repair.(4) Unfortunately, as the cartilage is avascular with low cell density, the healing potential is low when injury occurs.(5) Cartilage damage can either occur spontaneously (osteochondritis dissecans(6)), due to acute injury or chronically due to injury to another structure such as the anterior cruciate ligament and secondary instability.

Treatment options are broadly divided into those that aim to restore cartilage, such as microfracture and microfracture with scaffold insertion (AMIC) and those that aim to reduce symptoms without restoring cartilage e.g. debridement, focal resurfacing, osteotomy or joint replacement. Microfracture involves penetrating the subchondral bone at the time of surgery to release fibrin and marrow stem cells with the intention of stimulating cartilage formation.(7) Microfracture increases type II collagen, matrix and protein formation but not all components of articular cartilage leading to the suggestion that the addition of scaffolds, which are typically made of collagen, may further improve outcomes.(8) NICE guidance states that although the addition of a scaffold is not associated with safety concerns, current evidence for its efficacy is lacking in quantity and quality.(9) This NIHR-HTA commissioned study aims to address this evidence gap.

This trial was developed in collaboration with the University of Bristol Musculoskeletal Research Unit patient involvement group; the 'Patient Experience Partnership in Research (PEP-R) comprises nine members who have had, or are having, treatment for musculoskeletal health conditions, several of whom have had knee surgery. They suggested that this research was taken to them for their views in a larger group setting, rather than members attending trial management group meetings. They therefore felt that their contribution would be most efficient in the following ways: A) The group should discuss the project 6 times over the 5 year grant, with 2 meetings in the first year. B) At the start of the project, they will discuss study background, research methods, methodology and ethics. C) They will review the information for participants, including invitation letters, information sheet and consent form. D) They will review the questionnaires/outcome measures. E) They will advise on keeping participants engaged, including reviewing newsletters and the summary of results for participants. F) They will monitor the progress and conduct of the study and work with the study team to identify and prioritise next steps. G) At the final meeting, they will discuss how to communicate the results to a lay audience. H) The meetings will be organised and facilitated by an experienced patient and public involvement coordinator, [name] (co-applicant). She will attend the trial management group meetings. The group were happy for her to represent the group and provide feedback to them. She will provide ongoing support and tailored development to PEP-R members and advise researchers on good practice.

4. Aims and objectives

We hypothesise that in patients with symptomatic chondral or osteochondral defects of the knee requiring treatment, microfracture with microstructural scaffold leads to a superior Knee Injury and Osteoarthritis Outcome Score (KOOS) outcome at 2-years compared with microfracture alone. The overall aim of this study is to evaluate the clinical and cost effectiveness of microstructural scaffold in patients undergoing microfracture for a chondral or osteochondral defect of the knee.

Specific objectives of the trial are:

[figure not shown]
- 1. To estimate the difference between groups in mean Knee Injury and Osteoarthritis Outcome Score (KOOS) at 2 years
- 2. To estimate the difference between groups with respect to a range of secondary outcomes, including knee function, activity, Health Related Quality of Life (HRQoL), and return to work over a 2 year period
- 3. To estimate resource use and costs during the 2 year follow up and compare the costeffectiveness of microfracture plus scaffold (AMIC) versus microfracture alone

4. Establish systems to allow collection of longer-term outcomes from routinely collected data (e.g. need for knee replacement identified from Hospital Episode Statistics (HES)).

5. Plan of Investigation

5.1 Trial schema

Figure 1 Trial schema

5.2 Trial design

Multicentre, parallel group, superiority randomised controlled trial (RCT) in which participants and clinical care teams (except for staff involved in the surgery) and members of the research team responsible for data collection will be blinded to allocation.

Phase 1 (internal pilot) will determine the feasibility to randomise once debridement of the chondral/osteochondral lesion has been performed. Progression to Phase 2 will depend on showing satisfactory recruitment in Phase 1. All participants from phase 1 to 2 will be followed up for 24 months. Progression will be contingent on meeting the criteria defined in section 7.4.

Further follow up may continue for up to 10 years subject to further funding.

5.3 Setting

Patients will be recruited from secondary and tertiary care NHS hospitals.

5.4 Key design features to minimise bias

(a) Selection bias/allocation bias (systematic differences between baseline characteristics of the groups that are compared)

This bias is ruled out by concealed randomisation (see section 6.1). The allocation will not be revealed until sufficient information to uniquely identify the participant and establish eligibility has been entered into the trial database.

(b) Performance bias (systematic differences between groups in the care that is provided, or in exposure to factors other than the interventions of interest).

This bias will be minimised by:

- blinding all participants and the clinical care team not directly involved in the surgery and assessing the success of blinding (see section 6.2);
- defining the intervention and comparator, as well as standard protocols for other procedures undertaken during the trial (see section 5.6);
- defining procedures for participant follow-up (see section 6.11);
- monitoring adherence to protocol (see section 8.1 and 8.2).

The patient information leaflet (PIL) and the process of obtaining informed consent will describe the uncertainty about the effects of scaffold insertion. Therefore, in the event of inadvertent unblinding of a participant, he or she should not have a strong expectation that any one method should lead to a more favourable result.

(c) Detection bias (systematic differences between groups in how outcomes are determined)

This bias will be minimised by:

- The primary outcome is patient reported and the patients will remain blinded;
- blinding individuals assessing outcomes (see section 6.2).

(d) Attrition bias (systematic differences between groups in withdrawals from a study)

This bias will be minimised by:

- Using established Bristol Trials Centre (BTC) methods to maximise the proportion of participants for whom all outcome data are available, and the proportion of participants who receive the intervention to which they were allocated (see section 6.3.2).
- Implementing measures to promote adherence to random allocations (see section 7.1)
- Documenting non-adherence to random allocations (see section 7.1)
- Using intention to treat analysis and investigating sensitivity to attrition bias in statistical and economic analyses, implementing appropriate imputations for missing data (see sections 7.1 and 7.5).

(e) Reporting bias

This type of bias will be minimised by having pre-specified outcomes (see section 5.7) and a pre-specified analysis plan (see sections 7.1 and 7.5).

5.5 Trial population

Adults with symptoms arising from a chondral or osteochondral defect of the knee.

5.5.1 Inclusion criteria

Participant may enter the study if ALL of the following apply

- 1. 18 years of age or older
- 2. Symptomatic chondral or osteochondral defect of the knee sited on the medial or lateral femoral condyles, trochlea or patella as confirmed by standard clinical practice.
- 3. Chondral or osteochondral lesion measuring no more than 4cm²

5.5.2 Exclusion criteria

Participant may not enter the study if ANY of the following apply

- 1. Unstable, ligamentous injury to the knee that will not be treated
- 2. Unstable, meniscal tear that will not be treated
- 3. Less than 50% of native meniscal volume remaining in the knee following previous meniscal surgery
- 4. Knee alignment that in the opinion of the surgeon requires realignment surgery/osteotomy
- 5. Chondral or osteochondral lesion measuring >4cm² following operative debridement of the lesion to a stable chondral rim
- 6. Chondral or osteochondral lesion has been treated previously with one of the study interventions.
- 7. Defects occurring on the tibial chondral surface
- 8. Patient unable/unwilling to adhere to trial procedures
- 9. Unable to provide informed consent

10. Enrolled in another clinical trial and: a) co-enrolment is not permitted by the other trial; or b) co-enrolment would be burdensome for the patient; c) the intervention of the other trial could interfere with the SISMIC primary outcome.

5.6 Trial interventions

The surgery will be delivered in secondary or tertiary care facilities under the supervision of a Consultant Orthopaedic Surgeon. Participants will routinely have an MRI scan performed as part of their diagnostic/treatment pathway. All procedures will be performed in an operating theatre following preoperative assessment and appropriate consent, under general or regional anaesthesia according to the preference of the treating surgeon and anaesthetist.

Both trial interventions are stable, and it is not anticipated there will be significant change to the interventions during the trial. All study surgeons will deliver both study treatments.

A knee arthroscopy will be performed. The lesions will be identified and other pathology will be sought, assessed and recorded to ensure compliance with inclusion/ exclusion criteria. The chondral or osteochondral defect will be prepared according to the surgeon's standard technique, to ensure that the lesion is debrided adequately, removing all unstable chondral flaps to a stable chondral rim. The lesion will be measured to confirm it is not greater than 4cm² as per the eligibility criteria. A mini-arthrotomy (small incision) will be performed for access to the lesion where required. Microfracture will be performed to the exposed subchondral bone.

Surgeons that are already experienced in performing AMIC with an all arthroscopic technique will be permitted to continue to do so for patients randomised to the microfracture with microstructural scaffold (AMIC) arm of the trial. For those that are not experienced in performing AMIC with an all arthroscopic technique, the procedure will be performed through an arthrotomy. The specific technique used will be recorded

Intervention: microfracture of the chondral / osteochondral lesion with insertion of a bilayer collagen matrix microstructural scaffold (AMIC). The scaffold will be fixed either by stitching or using fibrin glue according to surgeon preference.

Control: microfracture alone.

5.6.1 Site and Surgeon Eligibility

If the study intervention (AMIC) is not routinely used at a site, the site's Trust Clinical Governance procedures should be followed to approve that the study intervention can be performed within the trust.

The techniques used in this study are stable clinical interventions that are in frequent and widespread use across the NHS. The skills required to perform the interventions are common to many of the procedures performed by the knee surgeons whom will deliver the study interventions. We recommend that the clinical expertise and competence of the Principal Investigator (PI) at each site to perform both study treatments is ensured by one of the following:

 Evidence of attendance of a surgical training day where arthroscopic chondral surgery was one of the techniques used within the last 2 years* or PI may provide confirmation of regular performance of arthroscopic chondral surgery (>4/year) in their clinical practice within the last 2 years.*

* excluding any period of cancelled or reduced activity in the NHS due to the effects of Covid19

If required, the Chief Investigator (CI) or Clinical Lead will sign off the PI to confirm their competency and eligibility for participation in the trial. Once participation in the trial is initiated, the CI or clinical lead may, if required, reconfirm competency within the first 6 months by at least one of the following:

- · attending the site to observe the performance of the study intervention or
- observing the surgeon perform the study intervention at a cadaveric (or alternative simulation environment) training session or
- review an intraoperative video of the technique being performed by the surgeon or
- observe videoed simulated delivery of the study intervention (either cadaveric or alternative simulation environment) or
- invite the PI to visit the sponsor site whilst study to observe the performance of the study intervention with training by the Clinical Lead

The site PI will confirm the competency of the other surgeons at their site. If any surgeon is not familiar with any part of the required interventions, face to face clinical training will be offered.

5.7 Primary and secondary outcomes

5.7.1 Primary outcome

Following the consensus statement recommendations of the International Cartilage Repair Society Recommendations, (10) the primary outcome is the participant-reported Knee injury and Osteoarthritis Outcome Score (KOOS) which is a validated score for articular cartilage repair 2 years post-randomisation.(11)

5.7.2 Secondary outcomes

Data will be collected to characterise the following secondary outcomes over the two year follow up period:

- 1. Knee function: International Knee Documentation Committee (IKDC) subjective knee evaluation score(12) at 2 years (range 0-100 with 100 representing the best level of symptoms, function and activity). Domains include symptoms experienced over the last 1-4 weeks and when undertaking particular activities, including sporting activities and activities of daily living. It is reliable and validated with a minimal clinically important difference (MCID) of 9 points.(13)
- 2. Activity: Tegner-Lysholm activity grading scale(14) (range 0-100 with 100 representing the best level of function/activity). There are 8 questions based on ability or symptoms including limp, support, pain, instability, locking, swelling, stair-climbing and squatting.
- 3. HRQoL: EQ-5D-5L, a validated, generalised and standardised instrument comprising a visual analogue scale measuring self-rated health and a health status instrument of 5 domains related to daily activities.(15) This instrument will be used to derived 2-year

- quality-adjusted life years (QALYs), by attaching UK preference-based utility indices to the EQ-5D-5L health states and weighting them with survival over time.
- 4. Productivity: Work Productivity and Activity Impairment (WPAI), a validated instrument which measures the impact of health and symptom severity on work productivity and non-work activities.(16) Absenteeism and presenteeism will be valued using the human capital approach and estimates of average weekly earnings(17) to estimate productivity losses for the economic evaluation.
- 5. Complications: to include bleeding, infection, deep vein thrombosis or pulmonary embolism, need for further surgery (non-joint replacement and joint replacement).
- 6. Resources required to i) deliver the two treatments, ii) treat short- and long-term complications; iii) follow-up care in hospital, including rehabilitation, outpatient appointments, A&E, and re-admissions. Other health and social care resources required in the community and patient expenditures with their care will be collected from the participant using questionnaires. Resources will be valued using Department of Health and Social Care reference costs, and national unit costs for health and social care, where available(18, 19), or local sources otherwise.

5.8 Sample size calculation

The MCID for the KOOS at 2 years is 10 points(20, 21) and the standard deviation (SD) is approximately 18 in the population of interest.(20, 21) A total sample size of 176 participants (88 per group) will provide 90% power to detect an effect size of 10/18 (=0.56) SD with 5% statistical significance (two-tailed), allowing for up to 20% loss to follow-up.

The sample size calculation has not accounted for the repeated administrations of the KOOS after surgery. Assuming that each participant completes at least two questionnaires over the two years of follow-up (and at baseline) and that there is a moderate correlation of 0.7 between the repeated scores, the study will have 90% power to detect a difference of 0.25 SD in a longitudinal analysis.

6. Trial methods

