6.11 Frequency and duration of follow up

Follow up will be face-to-face and via questionnaires. Questionnaires will be administered at at approximately 3, 6, 12 and 24 months post randomisation for information on knee function, activity, HRQoL, return to work and resource use.

Participants will attend the site for follow-up at approximately 3 months, 6 months, 1 year (all routine care) and at 2 years (research-specific follow-up). Data will be collected at these visits and with alternative arrangements for participants who do not attend (e.g. postal or on-line data collection, telephone follow-up at mutually agreed times).

All questionnaires will be administered by a research nurse at each participating centre in person, by post or online. Participating centres will be responsible for collecting these from patients and entering them into the study database. Reminders will be sent approximately 2 weeks after the initial contact if no reply has been received. A maximum of 3 reminders will be sent per time point. Participants can opt in to receive text message reminders. The SMS service will be provided by Three Cherries Limited, a third party vendor, contracted by the University of Bristol under a long-standing agreement to provide an SMS for research purposes.

Further follow up may continue for up to 10 years subject to further funding.

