6.12 Likely rate of loss to follow-up

Until discharge from hospital, the only losses to follow-up will be due to death, a participant withdrawing or ceasing to engage in follow-up; these losses are expected to be very few. In estimating the target sample size for the study, a loss to follow-up of 20% has been allowed for.

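### The claimed 90% power for 0.25 SD in the longitudinal analysis does not follow from the protocol's own inputs: it is about 79% with complete data and about 69% if 20% of participants are lost

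*Protocol*

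**What the plan says.** Section 5.8 makes two power statements.

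- **Main calculation.** "A total sample size of 176 participants (88 per group) will provide 90% power". The target there is a 10-point difference against an SD of 18, which is 0.56 SD; the test is two-sided at 5%, and one participant in five may be lost.
- **Longitudinal statement.** The next paragraph notes that the main calculation ignores the repeated KOOS. It assumes that every participant completes a baseline and at least two follow-up questionnaires and that "there is a moderate correlation of 0.7 between the repeated scores". On that basis "the study will have 90% power to detect a difference of 0.25 SD in a longitudinal analysis". It gives no formula, no separate significance level, and no indication whether 88 or about 70 per group was used.

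Three other sections bear on it. Section 6.12 repeats that "a loss to follow-up of 20% has been allowed for". Section 6.11 schedules questionnaires at "approximately 3, 6, 12 and 24 months post randomisation for information on knee function", so four follow-up scores are planned. Section 7.1 plans a mixed model adjusted for baseline, with an overall treatment effect reported unless the treatment-by-time interaction is significant at the 10% level.

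**The concern.** The longitudinal statement is a definite numerical claim, and its inputs are all on the page, so it can be checked without the SAP. A correlation as high as 0.7 limits what a second follow-up score adds, because the two scores largely repeat each other. Most of the gain has to come from baseline adjustment. Moving from 0.56 SD to 0.25 SD at the same power would require the variance to fall to about a fifth at the same number per group, or to about a quarter if complete data on 88 per group replace 70. That looked too large for these inputs.

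The mixed model is the planned analysis for outcomes measured repeatedly, and under section 8.3.2 the DMSC reviews the sample size assumptions. If the claim is too favourable, readers are told that the trial can reliably detect about 4.5 KOOS points when it cannot. A null overall effect could then be read as stronger evidence against a 0.25 SD difference than the design supports.

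**Working it through.** **Inputs** (section 5.8 unless noted): 88 per group; two-sided 5%; one baseline score; r ≥ 2 follow-up scores; correlation ρ = 0.7, taken as common to all pairs; SD 18; 20% loss (also section 6.12), giving 88 × 0.8 ≈ 70 per group; r = 4 scheduled (section 6.11); baseline-adjusted model (section 7.1).

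**1. The main calculation reproduces.** n per group = 2 × (1.960 + 1.282)² × (18/10)² = 2 × 10.507 × 3.24 = 68.1, so 69 by the normal approximation and 70 by the t-test. Then 70/0.8 = 87.5, rounded up to 88. Power at 70 per group is 90.8% (normal) or 90.4% (t). The same method is therefore a fair test of the second statement.

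**2. Longitudinal statement, two follow-up scores.** For the mean of r follow-up scores adjusted for one baseline score, the variance factor is

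F = (1 + (r − 1)ρ)/r − ρ²

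With r = 2: F = 1.7/2 − 0.49 = 0.36.

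The standard error of the difference, in SD units, is √(2F/n); power is Φ(0.25/SE − 1.960); the difference detectable with 90% power is 3.2415 × SE.

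- n = 88: SE = 0.0905; 0.25/SE = 2.764; power = Φ(0.804) = 78.9%; detectable difference 0.293 SD = 5.3 points.
- n = 70: SE = 0.1014; 0.25/SE = 2.465; power = Φ(0.505) = 69.3%; detectable difference 0.329 SD = 5.9 points.

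The t-distribution lowers these powers by about half a point (78.5% and 68.7%). To have 90% power for 0.25 SD: n = 2 × 0.36 × 10.507/0.0625 = 121.05, so 122 analysed per group.

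**3. Other readings of the same inputs** (power for 0.25 SD, two-sided 5%):

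| Analysis | F | 88 per group | 70 per group |
|---|---|---|---|
| Baseline-adjusted, r = 2 | 0.36 | 78.9% | 69.3% |
| Baseline-adjusted, r = 3 | 0.31 | 84.6% | 75.7% |
| Baseline-adjusted, r = 4 | 0.285 | 87.4% | 79.1% |
| Change score, r = 2 | 0.45 | 69.6% | 59.7% |
| Follow-up mean only, r = 2 | 0.85 | 43.6% | 36.1% |

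With r = 4 the detectable difference is 0.261 SD (4.7 points) at 88 and 0.293 SD (5.3 points) at 70. At 70 per group no number of follow-up scores reaches 0.25 SD: F cannot fall below 0.7 − 0.49 = 0.21, which gives 0.251 SD.

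A one-sided 5% test gives 86.8% with two scores at 88 per group. It passes 90% only with three or four scores and no loss (90.9% and 92.8%), and it contradicts the stated two-tailed test. A factor of (1 − 0.49)/2 = 0.255 gives 90.7% at 88, but it implies a correlation of 0.49 between the two follow-up scores, not 0.7. Whether the stated figure arose this way cannot be told from the protocol.

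**4. What would make 90% true with two scores.** A common correlation of 0.80 (88 per group) or 0.845 (70 per group). With 0.7 kept between follow-up scores, the baseline-to-follow-up correlation would have to be about 0.77 or 0.80. If it were instead 0.4 to 0.6 (an assumption; the protocol gives no separate value), the detectable difference would be 0.34 to 0.41 SD at 88 and 0.38 to 0.455 SD at 70.

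**The case against.** The strongest objections are about how large the error is, not whether there is one.

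- **The 20% loss belongs to the other paragraph.** The longitudinal sentence assumes that each participant completes two questionnaires, and a mixed model keeps anyone with some follow-up. A participant who misses 24 months may still have earlier scores. Summing information over participants at 88 per group: if 80% give four scores and 20% give three, 88 × (0.8/0.285 + 0.2/0.31) = 303.8 and power is 87%; if 80% give two and 20% give one (F = 0.51), 88 × (0.8/0.36 + 0.2/0.51) = 230.1 and power is 76%. This stands: 69% is the case in which 20% give no post-operative KOOS at all. The claim already fails at 88 per group without loss.
- **Two scores is a floor.** With four complete scores the shortfall is small: 87% against 90%, or 4.7 against 4.5 points. This also stands, but the sentence attaches its 90% to the two-score minimum, where the shortfall is 11 points.
- **The 0.7 may not cover baseline-to-follow-up pairs.** The protocol states one correlation for the repeated scores and counts the baseline among them, so a common value is the natural reading. A higher baseline correlation would rescue the claim; a lower one would worsen it. Neither is stated.
- **The statement is supplementary.** It did not set the sample size, every figure here lies well below the 10-point MCID, and results will be reported with 95% confidence intervals, which show what a null result excludes. This limits the harm but does not make the figure right.

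**Conclusion.** The statement is wrong as written. Under the protocol's own inputs, power for 0.25 SD is about 79% with two follow-up scores and complete data, so the type II error is 21% and not 10%. The difference detectable with 90% power is 0.29 SD. If 20% of participants contribute no post-operative score, the figures are about 69% and 0.33 SD. With all four questionnaires they are 87% and 0.26 SD with complete data, and 79% and 0.29 SD at 70 per group.

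This rests on a common correlation of 0.7, equal variance at each time point, a treatment effect constant over follow-up, and the normal approximation. The random effects for centre and surgeon are not allowed for in either direction. The main sample size of 176 for 0.56 SD is correct and not in question.

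**What to change.** Replace the last sentence of section 5.8. Suggested content: with one baseline and two post-operative scores, a common correlation of 0.7 and two-sided 5%, the study has 90% power for a time-averaged difference of 0.29 SD with complete data (88 per group), or 0.33 SD if 20% of participants give no post-operative score (70 per group); power for 0.25 SD is about 79% and 69% respectively. The four-score figures (0.26 and 0.29 SD) can be added. State the variance formula, and say whether 0.7 also applies between baseline and follow-up; if a different value is meant, give it and recompute. Make clear that the figure concerns the overall effect across time points and not the 2-year difference, which the main calculation covers.

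The cost is one reworded sentence and a less favourable stated figure. Sample size, recruitment and analysis do not change.
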